This study will be done in collaboration with [name] at the NIAAA.

c. Medications Employed in this Study:

In order to avoid fluctuating hormonal levels with subsequent menstruation, and to ensure reduction of gonadal steroids to hypogonadal levels during the withdrawal phase, suppression of ovarian function will be induced with the GnRH agonist leuprolide acetate (Lupron). As described in detail in protocol # 90-M-0088, Lupron is a synthetic nonapeptide that functions as an agonist that is 80 to 100 times more potent than natural GnRH in inducing the release of LH (79). During the first week of Lupron therapy, there is an initial increase in the pituitary release of LH and FSH leading to a transient increase in levels of the gonadal steroids estrone and estradiol in premenopausal females. However, within two to four weeks after initiation of treatment, there is a subsequent decrease in the number of GnRH receptors and an inhibition of pituitary elaboration of gonadotropins, leading to levels of estradiol similar to those observed in post-menopausal women.

Following suppression with Lupron, estradiol and progesterone will be administered in oral micronized form. The administration of 17 beta estradiol via an oral route using micronized E2 was chosen for this study because it has several advantages. First, it delivers the primary ovarian estradiol, into the circulation at a rate resulting in sustained levels of estradiol and

constant rates of excretion of estradiol conjugates (80). Second, at doses of 3-6 mg/day, it delivers sufficient estradiol into the circulation to raise estradiol plasma concentrations to levels similar to those of women around the ovulation phase of their menstrual cycle (80), levels that while far from reaching full pregnancy levels would give sustained supraphysiologic estradiol levels compatible with early pregnancy. Third, micronized estradiol has a short half-life, thus facilitating rapid reduction in plasma levels. Finally, the dose can be easily adjusted so that the presence of minor side effects such as nausea may not require complete cessation of the medication.

Orally administered micronized progesterone is biologically active and at doses of 600-1600 mg/day will result in plasma levels of 30-40 ng/ml (81,82). Progesterone in suppository form has been approved by the IRB for administration to patients with menstrual related mood disorders (MRMD) and controls under NIMH protocols # 92-M-0174, 90-M-0088.

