the minor depression module of the SADS-L. Urinary HCG will be determined to rule out pregnancy. Subjects who meet the inclusion criteria and who are medication free may be asked to return for follow-up interviews. During these interviews, phenomenological assessments may be performed by instruments such as the Premenstrual Tension Syndrome Scale (Steiner-Carroll Scale) (84), Beck Depression Inventory (85), Spielberger State-Trait Anxiety Inventory (86), Hamilton Rating Scales for Depression and Anxiety (87), Edinburgh Postnatal Depression Scale (88)) and related psychological measures. Additionally, subjects will be asked to fill out symptom self-rating scales, a modified version of the Daily Symptom Rating Form (Halbreich and Endicott) (89) and visual analogue scales (90), on a daily basis. During screening in protocol 81-M-0126 all subjects will receive a careful medical screening and will be excluded if there is evidence of significant renal, cardiac, hepatic, or other medical disorder. All patients will receive routine physical and laboratory examinations such as urinalysis, hematocrit, hemoglobin, BUN, creatinine, liver function tests, electrolytes, HIV, and a serum pregnancy test. Additionally, all women will have a normal EKG, and a normal PAP and gynecologic exam within the past year.

Subjects will be seen at the outpatient clinic on a regular biweekly basis. (Total = three baseline and 15 visits during treatment and follow-up.) During clinic visits, subjects will be monitored and managed for side effects, and blood samples will be drawn.

Research Procedures: Following the baseline period patients will receive 3.75 mg of the gonadotropin releasing hormone (GnRH) agonist leuprolide acetate (Lupron) during the early follicular phase of the menstrual cycle via intramuscular injection on a monthly basis in our clinic for five months. During the first two months of GnRH agonist administration, all subjects

will receive placebo progesterone and placebo estradiol tablets and will be told that at some point the placebo pills will be switched to active medication.

After the second month of Lupron-alone treatment, active estradiol and progesterone replacement will be initiated. Subjects shall be randomly assigned to one of two groups, and treatment shall be administered as follows:

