Lupron: The most frequent adverse effect of Lupron is hot flushes (flashes) reportedly occurring in 4-89% of patients receiving the drug. Lupron-induced hot flushes have ranged in severity from occasional mild flushing to frequent sweating. Episodes of flushing appear to decrease with continued therapy in most patients receiving Lupron; however, in at least one study, the incidence of hot flushes did not appear to decrease with continued therapy. In a recently completed study of 400 women of reproductive age with either uterine fibroids or endometriosis who each received 3.75 mgs depot Lupron every month for a period of six months, the most common side effects reported to occur were as follows: 1) hot flashes of mild to moderate intensity (89%), 2) headache (22%), 3) nervousness or irritability (11%), and 4) insomnia (10%). Local irritation at the injection site was complained of in less than 10% of the patients in this sample, and there was a mean decrease in bone density, as measured by bone densitometry, of 3.4 to 4.0%, which totally reversed after the medication had been discontinued for six months. Approximately ten patients of the original sample of 400 found the side effects to be severe enough to discontinue therapy. In the majority of women regular menstrual cycle function returned within two months following the last injection of depot Lupron (Tapp Pharmaceuticals, personal communication). Blurred vision, myalgias, lethargy, memory

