**10. Statistical Analysis:**

Analysis of Data: A repeated measures design has four groups of ten subjects each for a total of forty subjects. Each subject is measured during the hypogonadal baseline, at the end of the two months of addback, and during the following month (i.e., continued addback in group 2 or withdrawal in group 1). The effect of hormonal addback and withdrawal in subjects and controls on mood and biological parameters will be calculated using ANOVA-R with post-hoc Bonferroni t-tests.

Sample Size Justification: Based on previous data (61), the between-subject standard deviation is 0.69 and the within-subject standard deviation is 0.28. This design achieves 67% power when an F test is used to test the Groups factor at a 5% significance level and the actual standard deviation among the appropriate means is 0.30 (an effect size of 0.43), achieves 81% power when an F test is used to test the Times factor at a 5% significance level and the actual standard deviation among the appropriate means is 0.16 (an effect size of 0.57), and achieves 60% power when an F test is used to test the group by time interaction at a 5% significance level and the actual standard deviation among the appropriate means is 0.13 (an effect size of 0.46).

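### Section 10 takes the Lupron-alone phase as its only reference and gives the untreated pre-Lupron baseline no role, so a Lupron-induced patient-control gap cannot be told from a pre-existing one

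*Combined protocol and SAP*

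**What the plan says.** Section 10 (Statistical Analysis) names three occasions. The list opens with "Each subject is measured during the hypogonadal baseline" and goes on to the close of the addback phase and the month after it. The first is the two-month phase of Lupron with placebo capsules described under Research Procedures in section 4. Section 10 does not say which weeks of that phase supply the value. It names no covariate, and the planned analysis is ANOVA-R with Bonferroni post-hoc t-tests.

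The Introduction (subsection c, Medications Employed in this Study) says that in the first week of Lupron "there is an initial increase in the pituitary release of LH and FSH leading to a transient increase in levels of the gonadal steroids". Levels like those after menopause follow within two to four weeks.

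Section 4 also provides for an untreated period. All women complete visual-analogue self-ratings before treatment, with a two-month set reviewed by staff. Three baseline visits are counted apart from the 15 treatment and follow-up visits, and the first injection comes after the baseline period. Daily ratings then continue through the trial and are an outcome in section 9. Other pre-treatment scales (Beck, Hamilton, Edinburgh and others) are worded as optional.

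**The concern.** The reference point is itself a change in the hormones under study. The Introduction argues that women with past postpartum depression are differentially sensitive to changes in gonadal steroid levels, and Lupron alone produces one. Section 7 also lists nervousness or irritability (11%) and insomnia (10%) among Lupron effects in a study of 400 women with fibroids or endometriosis. These overlap with what the mood scales measure.

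If patients and controls differ at the hypogonadal point, the planned analysis cannot say whether they already differed before Lupron. Interpretation of the patient-control comparison and of changes from that point is at stake. The plan already reports an ambiguous patient-control difference during addback in its preliminary results, so the question has arisen in this paradigm before. The data that would help are at least partly collected.

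**Working it through.** **1. The plan's own figures.** Section 10: "A repeated measures design has four groups of ten subjects each for a total of forty subjects", and "the between-subject standard deviation is 0.69 and the within-subject standard deviation is 0.28". The effect sizes check: 0.30/0.69 = 0.43, 0.16/0.28 = 0.57, 0.13/0.28 = 0.46. The stated powers (67%, 81%, 60% for Groups, Times, Group x Time) do not reproduce. With a noncentral F and noncentrality 40 x f², they come out at 57.5%, 89.7% and 52.5%. That is a separate matter. It is noted only because step 4 uses this convention and so starts from 53%, not 60%.

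**2. What the reference does to a change score.** Let b be the excess of the untreated-to-Lupron shift in patients over that in controls. For any later occasion L:

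(L − untreated) − (L − hypogonadal) = hypogonadal − untreated.

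In the patient-control difference this equals b. The plan never forms the right-hand side, so b is invisible. Two contrasts contain no hypogonadal value or share it equally:
- Withdrawal minus end of addback: the hypogonadal value does not enter.
- Month-5 withdrawal versus continuation: arms are randomised and both have the same Lupron-alone phase, so b is balanced in expectation.

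**3. Size of b on the interaction scale.** Assume the four groups are two diagnoses by two arms, and that b appears only at the first occasion. The interaction terms are ±(b/2) x (2/3, −1/3, −1/3). Their mean square is (b²/4) x (4/9 + 1/9 + 1/9)/3 = b²/18, so the SD among means is b/√18 = 0.236b.
- b = 0.1: 0.024, which is 18% of the planned 0.13.
- b = 0.28 (one within-subject SD): 0.066, which is 51% of 0.13.

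Both values of b are illustrations; no document gives one.

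**4. Ways to use the untreated baseline.**

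*As a fourth time level* (same f, noncentrality 40 x f²): Times power 90% → 86%; Group x Time 53% → 45%; all-pairs comparisons 3 → 6, Bonferroni level 0.0167 → 0.0083.

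*As a covariate in the month-5 comparison*, beside the hypogonadal value and assuming compound symmetry:
- Total variance: 0.69² + 0.28² = 0.4761 + 0.0784 = 0.5545.
- Correlation: rho = 0.4761/0.5545 = 0.86.
- k baselines explain R² = k·rho²/(1 + (k − 1)·rho).
- k = 1: R² = 0.737; residual SD = √(0.5545 x 0.263) = 0.38.
- k = 2: R² = 0.793; residual SD = √(0.5545 x 0.207) = 0.34.
- Detectable difference, 10 per arm, 80% power, two-sided 5%, normal approximation: (1.960 + 0.842) x SD x √(2/10) = 1.253 x SD, giving 0.48 for k = 1 and 0.42 for k = 2.

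**The case against.** The hypogonadal reference was chosen for a reason. It is the same Lupron-plus-placebo regimen to which the withdrawal arm returns in month 5, whereas the untreated state differs in cycling hormones, injection and capsules. That stands, and the hypogonadal value should stay. The trial's current question, withdrawal versus continued exposure, is answered by the randomised month-5 comparison, which this choice does not bias. That stands too.

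Controls are measured at the same point, so a patient-control gap there would be visible in the group means. Also true: only its origin is hidden.

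Untreated values are no clean yardstick either. Women are screened for absence of significant symptoms, so regression to the mean could look like a Lupron effect. This limits the added contrast but does not make it useless.

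A reader might infer that the reference is contaminated by the early rise, because two to four of about eight weeks (25-50%) may precede full suppression. The documents do not support that. Section 10 does not say that the whole phase is averaged, and calling the baseline hypogonadal points past those weeks. It is an undefined window.

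**Conclusion.** The gap is real and limited. Section 10 leaves available untreated data unused and cannot separate a pre-existing patient-control difference from one induced by Lupron. Changes from the hypogonadal point differ from changes from the untreated state by b, whose size and sign are unknown.

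Three stronger readings should not be drawn:
- That the withdrawal finding is biased: neither the month-5 contrast nor withdrawal minus end of addback is.
- That a shift of 0.1 nearly matches the planned 0.13: on the same scale it is about 0.024.
- That the Lupron-induced estradiol fall is a known fraction of the fall from addback: the flare level is not given, and Lupron starts in the early follicular phase.

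The precision gain (0.48 to 0.42) assumes compound symmetry with rho 0.86, and an analysis that already adjusts for the hypogonadal value, which section 10 does not state. It shrinks if untreated scores sit near the floor, as selection makes likely.

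**What to change.** In section 10:

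1. Keep the hypogonadal value as the same-state comparator for withdrawal. As a clarification, state its weeks, for example Lupron weeks 5-8, which lie beyond the protocol's own suppression time.
2. For outcomes with pre-Lupron data, add each woman's mean untreated baseline as a covariate in the month-5 comparison. Daily self-ratings qualify for all women; the rating scales only where they were done. Blood draws are counted for 15 visits only, so untreated hormone values are not assured.
3. Pre-specify one contrast, untreated to Lupron-alone by diagnosis, with a stated caution about selection for absence of symptoms and regression to the mean.
4. Do not add the untreated baseline as a fourth time level, given the loss of interaction power and the doubled comparisons.

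Cost: one degree of freedom and one extra contrast, with no new visits. Initial screening runs under a separate protocol (81-M-0126), so the text should confirm that ratings made there may be used and are on the same items as the in-trial ratings.

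### Minor, nearly free improvement: replace single-step Bonferroni in section 10 by Holm's step-down, and list the contrasts that form the family

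*Combined protocol and SAP*

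**What the plan says.** Section 10 (Statistical Analysis) describes the design as follows: "A repeated measures design has four groups of ten subjects each for a total of forty subjects". On timing it says: "Each subject is measured during the hypogonadal baseline, at the end of the two months of addback, and during the following month". Mood and biological parameters are to be analysed by repeated-measures ANOVA with "post-hoc Bonferroni t-tests". The section does not list the post-hoc contrasts or their number, does not say whether the family spans outcomes, and mentions no step-down version.

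The sample-size paragraph gives the variability: "the between-subject standard deviation is 0.69 and the within-subject standard deviation is 0.28". Its power figures are all for omnibus F tests at 5%: 67% for groups, 81% for times and 60% for the interaction. No power is stated for any post-hoc comparison.

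The only other multiplicity method in the document is false discovery rate control, under the analysis of RNA sequencing data in section 1, and it is confined to that analysis. Section 9 lists several rating scales, daily ratings, hormone measures, expression data and a stimulation test, and names no primary outcome.

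Section 3(a) gives a different enrolment from section 10: 40 women with past postpartum depression (PPD), 20 with past major depression and 40 controls, 100 in all.

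**The concern.** The central question, in sections 1(b) and 2, is whether withdrawal of the hormones or prolonged exposure to them produces symptoms. An omnibus F test over four groups cannot say which cells differ, so the answer runs through the post-hoc tests. The plan's own power is modest before any post-hoc correction is applied (67% for groups, 60% for the interaction).

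Single-step Bonferroni holds every comparison to 0.05/m, where m is the number of comparisons, even after some have already been rejected. Holm relaxes the threshold after each rejection at no cost in family-wise error. What is at stake is a little power on the second and later contrasts. The validity of the analysis is not in question.

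**Working it through.** **1. The plan's own figures.** The effect sizes check: 0.30/0.69 = 0.435, 0.16/0.28 = 0.571, 0.13/0.28 = 0.464. The standard noncentral F calculation (λ = N·f², N = 40; df 3 and 36, 2 and 72, 6 and 72; α = 0.05) gives 57.5%, 89.7% and 52.5%, against the stated 67%, 81% and 60%. Rounding of the inputs gives only 55–60%, 86–92% and 47–58%. The stated powers therefore do not reproduce. That is a separate matter: they concern omnibus tests and do not depend on the post-hoc correction.

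**2. Why Holm never rejects less.** Order the m p-values. Bonferroni compares each with 0.05/m. Holm compares the i-th smallest with 0.05/(m − i + 1) and stops at the first failure. For m = 6:

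| Rank | 1 | 2 | 3 | 4 | 5 | 6 |
|---|---|---|---|---|---|---|
| Bonferroni | 0.0083 | 0.0083 | 0.0083 | 0.0083 | 0.0083 | 0.0083 |
| Holm | 0.0083 | 0.0100 | 0.0125 | 0.0167 | 0.025 | 0.05 |

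Every Holm threshold is at least the Bonferroni one. The first thresholds are equal, so the chance of at least one rejection in the family is identical.

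**3. Why the error rate holds.** If m₀ hypotheses are truly null, the smallest null p-value has rank at most m − m₀ + 1, so its Holm threshold is at most 0.05/m₀. The union bound over m₀ nulls gives at most 0.05, with no assumption about dependence.

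**4. Size with one shifted cell.** Inputs from section 10: ten per cell, three times, standard deviations 0.69 and 0.28. Assumptions: independent within-subject errors; only the past-PPD withdrawal cell shifts, in the final month, by 0.2 to 0.5; m = 3, 4, 6 or 12, because the family is undefined. Power for the key contrast (%), Bonferroni → Holm:

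| m | 0.2 | 0.3 | 0.4 | 0.5 |
|---|---|---|---|---|
| 3 | 14.8 → 16.1 | 35.1 → 38.3 | 61.1 → 65.6 | 82.8 → 86.7 |
| 4 | 7.3 → 7.7 | 16.7 → 17.6 | 33.3 → 35.2 | 53.3 → 55.9 |
| 6 | 5.5 → 5.8 | 13.0 → 14.0 | 27.5 → 29.7 | 46.7 → 49.7 |
| 12 | 5.4 → 5.5 | 16.0 → 16.2 | 36.3 → 36.9 | 59.1 → 60.0 |

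The largest gain is 65.6 − 61.1 = 4.5 points and the smallest 5.5 − 5.4 = 0.1. The chance of detecting every true contrast rises by up to about 6 points. Holm missed no Bonferroni rejection in any simulated data set, and its family-wise error stayed at or below 5% (m = 6, shift 0.5: 2.2% for Bonferroni, 3.1% for Holm).

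**5. Six pairwise comparisons at the final month.** Pooled error on 36 df.
- Unadjusted standard deviation: √(0.69² + 0.28²) = √0.5545 = 0.745.
- Implied correlation between times: 0.4761/0.5545 = 0.859.
- Baseline-adjusted standard deviation: 0.745 × √(1 − 0.859²) ≈ 0.38.

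At 0.745, gains are about 1 to 3 points. At 0.38 with one cell shifted by 0.64, power goes from 83% to about 85–86%. At 0.38 with assumed means of 0.9 (past PPD, withdrawal), 0.3 (past PPD, continued) and 0 in both control cells, withdrawal v continuation goes from 76% to 83%, and continued past PPD v control from 17% to 25%.

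**6. How these scenarios compare with the planned interaction of 0.13.** A single shift of 0.64 gives 0.64 × √[(3/4)(2/3)/12] = 0.131, which matches. The two-effect means have deviations 0.6, 0, −0.3, −0.3 and sum of squares 0.54, giving √(0.54 × (2/3)/12) = 0.173, about a third larger than planned.

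**7. Twenty per cell** (section 3(a), assuming an even split of the past-PPD and control groups). Holm still never loses. In the one-shift setting of step 4 its gain is about 0.1 to 4 points; in the favourable setting of step 5, continued past PPD v control goes from 42% to 55%.

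**The case against.** Bonferroni is valid, simple and prespecified, and it yields matching simultaneous confidence intervals. Preferring Holm chooses between two valid procedures and corrects no error. No power figure in section 10 moves. All of that stands, and it is why the point is minor.

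A reader might infer that the plan forgoes 7 to 8 points of power. The documents do not support that. The figure needs a baseline-adjusted standard deviation that section 10 does not plan, and assumed means that imply a larger interaction than the one planned.

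A reader might also infer that several true effects are expected together, which is where Holm gains most. Section 1(b) does report that women with past PPD were more symptomatic than controls during addback as well as withdrawal, so the pattern is possible. But sections 1(b) and 2 pose withdrawal and prolonged exposure as rival explanations. If continued exposure produced equal symptoms, withdrawal v continuation would be a true null.

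Nor is the power irrecoverably lost, since the choice can be amended before analysis without new data.

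Two further objections stand and shape the fix. Holm's later thresholds depend on which contrasts are in the family, and section 10 defines none, so changing the name of the correction alone leaves the procedure undefined. And Bonferroni intervals can include zero for a contrast that Holm rejects.

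**Conclusion.** The point holds as a minor efficiency improvement. Single-step Bonferroni is valid but needlessly conservative, because Holm gives the same 5% family-wise control under any dependence and never rejects less.

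At ten per cell the expected gain for one contrast is about 0 to 4.5 points. Gains of 7 to 8 points are conditional on coexisting effects and baseline adjustment, and should not be taken as the expected benefit. All sizes rest on assumed shifts and an assumed family, because the plan defines neither for the post-hoc tests. Holm's dominance rests on no such assumption.

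Defining the family matters more than the choice between the two corrections. The ten per cell in section 10 and the 100 women in section 3(a), who include a third diagnostic group absent from the four-group design, must be reconciled, but Holm is never worse at either size.

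**What to change.** In section 10, replace the post-hoc wording by *post-hoc t-tests with Holm step-down adjustment at a 5% family-wise level*. In the same place, list the contrasts that form the family and say whether it is defined per outcome or across outcomes. One possible list, all at the final month, is withdrawal v continuation within past PPD, and past PPD v control within each regimen. Fix this before outcome data are examined, so that the change cannot look data-driven.

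If simultaneous intervals are wanted, keep the Bonferroni ones and state that they may not match every Holm decision. Reconcile the group structure and cell sizes of section 10 with section 3(a), since the list of contrasts depends on them.

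The cost is one phrase and a short list. No additional participants, visits or data are needed.

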**3. Subjects:**

**a) Description of Study Populations:**

This study will enroll -40 asymptomatic women with a past postpartum depression, 20 asymptomatic women with a past major depression (not related to the postpartum), and 40 asymptomatic women with no past Axis I psychiatric illness.

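### The stated powers of 67%, 81% and 60% are not reproduced for four groups of ten on three occasions; with λ = N·f² the printed effect sizes give about 56%, 90% and 52%

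*Combined protocol and SAP*

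**What the plan says.** Section 10 (Statistical Analysis) describes the design as follows: "A repeated measures design has four groups of ten subjects each for a total of forty subjects". On the occasions it says: "Each subject is measured during the hypogonadal baseline, at the end of the two months of addback, and during the following month". The analysis is a repeated-measures ANOVA with post-hoc Bonferroni t-tests.

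The sample size paragraph takes its variability from earlier data: "the between-subject standard deviation is 0.69 and the within-subject standard deviation is 0.28". It then gives three powers:

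- Groups: "This design achieves 67% power when an F test is used to test the Groups factor at a 5% significance level", for an SD among means of 0.30 and an effect size of 0.43.
- Times: "achieves 81% power when an F test is used to test the Times factor at a 5% significance level", for an SD among means of 0.16 and an effect size of 0.57.
- Interaction: "achieves 60% power when an F test is used to test the group by time interaction at a 5% significance level", for an SD among means of 0.13 and an effect size of 0.46.

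The section gives no noncentrality formula, within-subject correlation, sphericity assumption, outcome scale or software.

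Section 3a sets enrolment at 40 women who have had postpartum depression before, together with these two further groups: "20 asymptomatic women with a past major depression (not related to the postpartum), and 40 asymptomatic women with no past Axis I psychiatric illness".

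**The concern.** The paragraph prints nearly everything a power calculation needs: group sizes, occasions, significance level, SDs and effect sizes. The powers should therefore follow from it. They do not, and under the most direct convention they miss in both directions: Groups and interaction come out lower than stated, Times higher. A single change of sample size or significance level would not explain that.

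These are the only operating characteristics in the plan. If they do not belong to the design they are attached to, a reader cannot tell how sensitive the study is.

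**Working it through.** **Inputs (section 10).** N = 40, four groups of ten, three occasions, two-way repeated-measures ANOVA, α = 0.05. The degrees of freedom follow: Groups (3, 36), Times (2, 72), interaction (6, 72).

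**Step 1: the effect sizes reproduce.** 0.30/0.69 = 0.435, 0.16/0.28 = 0.571 and 0.13/0.28 = 0.464, printed as 0.43, 0.57 and 0.46.

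**Step 2: the powers do not.** Power = P(F′(u, v, λ) > F₀.₉₅(u, v)), with F′ noncentral F, λ = N·f² and sphericity.

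| Test | λ from printed f | Power | Power, unrounded ratio | Stated |
|---|---|---|---|---|
| Groups | 40 × 0.43² = 7.40 | 56.5% | 57.5% | 67% |
| Times | 40 × 0.57² = 13.00 | 89.5% | 89.7% | 81% |
| Interaction | 40 × 0.46² = 8.46 | 51.7% | 52.5% | 60% |

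Simulation of the 4 × 10 x 3 ANOVA (20,000 runs), with a residual SD of 0.28·√3 so that λ = N·f² holds, gave 58.2%, 89.9% and 52.7%.

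**Step 3: other readings of 0.69 (Groups).** In each, λ = 40 × 0.30² / (variance of a subject's mean).

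- SD of subject means: 55.4 to 57.5% for any f that rounds to 0.43.
- Random-intercept SD: variance 0.69² + 0.28²/3 = 0.502, λ = 7.17, power 55.0%.
- Single-occasion total SD with residual SD 0.28: variance 0.69² − 0.28² + 0.28²/3 = 0.424, λ = 8.49, power 63.1%. With 0.305, 0.685 and 0.285 in place of 0.30, 0.69 and 0.28, λ = 8.96 and power is about 66%.
- Variance 0.69² + 0.28²: λ = 6.49, power 50.5%.

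67% needs λ = 9.21.

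**Step 4: another reading of 0.28.** If it is the residual SD at a single occasion, λ = 3·N·f². Times: 120 × 0.57² = 38.99, power above 99.9%. Interaction: 120 × 0.46² = 25.39, power 97.0%. Both now lie above the stated figures, whereas in step 2 the interaction lay below.

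**Step 5: Times against interaction.** The two tests share one error term, so the ratio of their noncentralities does not depend on 0.28. Powers of 81% and 60% need λ = 10.29 and 10.01, a ratio of 1.03.

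- SDs among means with divisor k (3 times, 12 cells): the ratio is (40 × 3 × 0.16²)/(10 × 12 × 0.13²) = 3.072/2.028 = 1.51. Times at 81% then implies an interaction λ of 10.29/1.51 = 6.79, power about 42%. Interaction at 60% implies a Times λ of 10.01 × 1.51 = 15.16, power about 94%.
- Sample SDs (divisors 2 and 11): the ratio is (40 × 2 × 0.16²)/(10 × 11 × 0.13²) = 2.048/1.859 = 1.10. Times at 81% goes with interaction of about 56%, and interaction at 60% with Times of about 84%. Groups then has λ = 10 × 3 × 0.30²/0.69² = 5.67, power about 45%.

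**Step 6: the enrolled numbers.** Assume the 40 women with past postpartum depression and the 40 controls form four groups of 20. With λ = 80·f², the printed effect sizes give 89.7%, 99.7% and 87.5%.

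**The case against.** The strongest reply is that the plan leaves its conventions open, and that the definitions may lie in the earlier study it cites. Much of this stands, and it rules out several stronger readings.

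- **That 81% and 60% contradict each other whatever 0.28 means.** A reader might infer this from the ratio of 1.51, but it needs divisor-k SDs among means, which the plan does not state. With sample SDs, rounding of 0.16 and 0.13 lets the ratio run from 0.96 to 1.27, which contains 1.03. That reading helps only this pair, since it takes Groups further from 67%.
- **That Times is understated and the interaction overstated.** This holds under λ = N·f² but not if 0.28 is a per-occasion residual SD.
- **That Groups can never reach 67%.** If 0.69 is a single-occasion SD and the correlation is left free instead of being set by 0.28, a correlation of 0.5 gives a variance of 0.4761 × 2/3 = 0.317, λ = 11.34 and power 76.9%. But the effect size would then be 0.53, not 0.43. A correlation of about 0.73 gives 67%, but it implies a residual variance of 0.4761 × 0.269 = 0.128 and hence a Times λ of 3.072/0.128 = 24, power about 99%. The three figures still do not come out together.
- **That the figures belong to two groups.** Two groups of 16 on three occasions give 65.3%, 81.1% and 61.7% from the printed effect sizes. The closeness is notable, but the plan states four groups and mentions no such layout.
- **That 60%, or 52%, is the power to compare withdrawal with continuation.** The omnibus interaction on 6 degrees of freedom includes that fifth-month contrast (section 4d), but its power is not the power of the contrast.

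It is also fair that the plan sets no power target and openly reports values below 80%.

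**Conclusion.** The concern holds as a failure to reproduce: no reading tried of four groups of ten on three occasions yields 67%, 81% and 60% together. Under λ = N·f² with sphericity, Groups is overstated by about 10 points (67 against 56.5), the interaction by about 8 (60 against 51.7), and Times is understated by about 8 (81 against 89.5).

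The Groups shortfall is the firmest part. It rests on 0.69 being the SD of subject means, as the printed effect size implies, or on 0.28 being the residual SD. For Times and the interaction the mismatch stands, but its size and direction cannot be settled until 0.28 and the SD among means are defined. The mutual inconsistency of that pair is conditional on divisor-k SDs.

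No analysis is invalidated. The paragraph should be corrected because it is the plan's only statement of power, and because it may describe a smaller study than the one section 3a enrols.

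**What to change.** 1. Reconcile the four groups of ten in section 10 with the 40 + 20 + 40 women in section 3a, and say where the past-major-depression group enters the analysis.
2. Define 0.69 and 0.28 (for example random-intercept and residual SD, or SDs of subject means), the divisor used for the SD among means, and the outcome scale.
3. Recompute all three powers for that one design, and restate them with the noncentrality formula and the sphericity assumption.

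The figures 56/90/52 should go in only if 4 × 10 × 3, λ = N·f² and sphericity are all confirmed.

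The cost is one calculation and one rewritten paragraph. The downside is that, if 4 × 10 is kept, the stated Groups power falls to about 56 to 57% under that convention. If instead four groups of 20 are confirmed, the powers rise to the values in step 6 of the working.
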